4.2.2 Inclusion Criteria

1. Is male or female, aged 18 to 65 years (inclusive) at screening.
2. Capable of giving signed informed consent, able to understand and comply with protocol requirements, instructions, and protocol-related restrictions, and likely to complete the study as planned.
3. Has a body mass index 19.0 to 40.0 kg/m² (inclusive).

4. Is able to swallow capsules whole, without crushing, chewing, or opening.
5. Has a current diagnosis of MDD according to the DSM-5 for either recurrent or single episode MDD without psychotic features that is confirmed by the MINI at screening.
6. Has a MADRS score of ≥ 22 for the current major depressive episode (MDE) at screening and baseline (Day 1) before SM administration.
7. Has a CGI-S score of ≥ 4 (moderately ill or worse) at screening and baseline (Day 1) before SM administration.
8. Has been on a stable therapeutic dose of one of the following study-approved ADTs for the current MDE for ≥ 6 weeks prior to screening: citalopram, escitalopram, paroxetine, fluoxetine, sertraline, duloxetine, venlafaxine (immediate release or extended release), desvenlafaxine, vilazodone, levomilnacipran, vortioxetine, bupropion, or dextromethorphan/bupropion. Subject must be on antidepressant monotherapy before baseline.

Note: If a subject is taking a second ADT or augmentation therapy at screening, the investigator should decide if it is medically appropriate to discontinue the second drug before baseline. If so, the second drug should be discontinued for at least 5 half-lives prior to baseline. If not, the subject should be excluded from the study.

9. Agrees to maintain a stable therapeutic dose of the approved ADT throughout the study.
10. Non-pregnant female subjects of childbearing potential (FOCP) who are exclusively in a same-sex relationship are included without the need of acceptable birth control methods.
FOCP who are sexually active with a male partner (who is biologically capable of having children), must agree to use one of the following acceptable birth control methods after signing the informed consent form (ICF), throughout the study, and for 30 days following the last dose of SM:
 - a. Simultaneous use of male condom and intra-uterine contraceptive device placed at least 4 weeks prior to the first administration of SM.
 - b. Simultaneous use of a male condom and diaphragm with spermicide.
 - c. Established hormonal contraceptive (started at least 4 weeks prior to the first dose of SM).

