8.3 Handling of Dropout or Missing Data

For safety analyses, a missing date for an AE and non-study medication use will be imputed as described in the SAP. Missing data for all other safety endpoints will not be imputed.

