3.9.2. Missing Dates for Adverse Events and Concomitant Medication

Missing dates for adverse events (AEs) and concomitant medications will be imputed according to the rules in Table 3.

Table 3: Missing Date Imputation for Adverse Event or Concomitant Medication

Missing Date Pattern	Imputation Rule
Partial Start Date	
Missing day only: Impute the first dose date if (1) the year and the month of the event start date are identical to those of the first dose date and (2) the event end date is not prior to the first dose date; otherwise, impute the first day of the month.Missing month only: Impute the first dose month if (1) the year of the event start date is identical to the year of the first dose date and (2) the event end date is not prior to the first dose date; otherwise, impute January.Missing month and day: Impute the first dose date if (1) the year of the event start date is identical to the year of the first dose

Missing Date Pattern	Imputation Rule
	date and (2) the event end date is not prior to the first dose date; otherwise, impute 1 st January.
Partial End Date	
• Missing day only: Impute the last day of the month or the last study date, whichever is earlier.• Missing month only: Impute December or the month of the last study date, whichever is earlier.• Missing month and day: Impute 31st December or the last study date, whichever is earlier.
Missing Year or Completely Missing Date	No Imputation will be done.

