4.2. Protocol Deviations

A protocol deviation is defined as any change, divergence, or departure from the study design or procedures defined in the protocol. An important protocol deviation (IPD) is defined as a protocol deviation that might significantly affect the completeness, accuracy, and/or reliability of the study data or that might significantly affect a subject's rights, safety, or well-being.

Potential IPDs may include, but are not limited to:

- Subjects who received the study treatment but are later found not to have met all the inclusion criteria or met any of the exclusion criteria
- Subjects who received concomitant medications that were prohibited as described in Protocol Section 5.7

Occurrence of any of these and other events may be considered as potential IPDs. However, these events should be categorized as IPDs only if they could potentially affect interpretation of study results. Prior to the database lock, potential IPDs identified in the clinical database and/or recorded in the site deviation log will be reviewed for the determination of IPDs. All protocol deviations will be provided in subject data listings.

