4.5. Prior and Concomitant Medications

Prior and concomitant medications and antidepressant therapy (ADT) will be coded using WHO DRUG Global version SEP2023 with anatomical therapeutic chemical (ATC) classification and Preferred Name (PN). ATC fourth (ATC4) level is for the chemical, pharmacological or therapeutic subgroup. If a ATC4 level classification is not available for a coded term, the lowest available ATC level code will be substituted.

If a medication starts prior to the first dose and continues after the first dose, it will be considered both prior and concomitant. Prior and concomitant medications as well as ATDs will be summarized by ATC and PN, and also listed by subject ID using the Safety Population.

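### SAP Table 3 applies the adverse-event date rule to medications, so a start known only to the first-dose year becomes Day 1 and a pre-baseline stop in the first-dose month can be dated on study

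*SAP*

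**What the plan says.** SAP 3.9.2 puts both kinds of record under one set of rules: "Missing dates for adverse events (AEs) and concomitant medications will be imputed according to the rules in Table 3". Protocol 8.3 delegates the matter in wider terms: "a missing date for an AE and non-study medication use will be imputed as described in the SAP". The rules in Table 3 are worded for an event, and neither document gives a separate rule for medications.

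- **Start date, month and day missing:** "Impute the first dose date if (1) the year of the event start date is identical to the year of the first dose" date and, as a second condition, "the event end date is not prior to the first dose date". Otherwise 1 January of the recorded year is used.
- **End date, day missing:** "Missing day only: Impute the last day of the month or the last study date, whichever is earlier". There is no cap at first dose for a drug known to have been stopped earlier.
- **Classification (SAP 4.5):** "If a medication starts prior to the first dose and continues after the first dose, it will be considered both prior and concomitant".
- **Background therapy (Protocol 4.2.2, Inclusion 8):** a stable, therapeutic dose of one of the "study-approved ADTs for the current MDE for ≥ 6 weeks prior to screening".
- **Deviations (SAP 4.2):** one of the two listed examples of a potential important deviation is "Subjects who received concomitant medications that were prohibited as described in Protocol Section 5.7".

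**The concern.** Moving a partial start date to first dose is cautious for an adverse event: when in doubt, the event counts as treatment-emergent. A medication has no such cautious direction. A drug written down at screening started before Day 1, so a Day 1 start contradicts the record. The end-date rule errs the other way, because it can extend a drug stopped for the study into the dosing period.

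This is an uncontrolled study on top of stable antidepressant therapy (ADT). Readers will use the medication summaries to judge whether background treatment was constant and whether excluded drugs had really been stopped. With about 50 subjects, a few misclassified records would be visible.

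**Working it through.** The documents state no figure on this point, so there is nothing to reproduce. The check applies the Table 3 rules to dates.

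**Inputs.** ADT stable for at least 6 weeks = 42 days before screening (Inclusion 8). Screening from Day -28 to Day -1 (Protocol 4.1). Tapering or stopping a drug only after consent (Protocol 5.7.2), so stops made for the study fall within screening. Assumptions: the last study date is Day 12, an ongoing drug meets the second start-date condition, and dosing is in 2024 (Protocol version 3.0 is dated 14 February 2024).

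**1. Size of the start-date error for an eligible ADT.** Minimum gap between true start and Day 1 = 42 + 1 = 43 days; with a 28-day screening, 42 + 28 = 70 days.

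Example: Day 1 on 17 Jun 2024, screening 28 days earlier on 20 May, ADT start recorded as 2024 only. The latest eligible start is 20 May − 42 days = 8 Apr; the earliest consistent start is 1 Jan. Table 3 gives 17 Jun. The error lies between 22 + 31 + 17 = 70 days and 31 + 29 + 31 + 30 + 31 + 16 = 168 days.

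**2. When the start rule does no harm.** A start recorded as 2023 becomes 1 Jan 2023, and the drug stays both prior and concomitant. A start recorded as March 2024 becomes 1 Mar 2024. An eligible ADT with only the day missing is never moved to Day 1, because a gap of at least 43 days cannot fit within one calendar month.

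**3. How often a year-only ADT start would reach the Day 1 branch.** Take Day 1 as uniform from 14 Feb to 31 Dec 2024 (366 − 44 = 322 days). A true start G days earlier falls in the same year when the day of the year of Day 1 exceeds G. The share is 100% for G = 43, and (366 − G)/322 for larger G:

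- G = 70: 296/322 = 92%
- G = 90: 276/322 = 86%
- G = 180: 186/322 = 58%
- G = 365: 1/322, about 0%

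**4. End-date rule.** The imputed stop is the earlier of month-end and the last study date. Both fall on or after Day 1 whenever the stop month is the Day 1 month. With Day 1 on 17 Jun 2024, Day 12 is 28 Jun:

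- Stop in June 2024, day missing: min(30 Jun, 28 Jun) = 28 Jun, so the drug appears to have been taken throughout.
- Stop in May 2024, day missing: 31 May, correctly before Day 1.

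A stop g days before Day 1 (g from 1 to 28) is in the same month when the day of the month of Day 1 exceeds g. Over all 366 possible Day 1 dates in 2024, the share imputed on or after Day 1 is (366 − 12g)/366:

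- g = 1: 354/366 = 97%
- g = 7: 282/366 = 77%
- g = 14: 198/366 = 54%
- g = 28: 30/366 = 8%
- average over 1 to 28, equally weighted: 1 − 12 × 14.5/366 = 52.5%

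These shares in steps 3 and 4 apply only to records that have the partial date in question. The documents give no count of such records.

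**5. What the imputed dates feed.** SAP 4.5 uses them for prior/concomitant status. An ongoing drug moved to Day 1 loses prior status but stays concomitant. A stopped drug moved past Day 1 gains concomitant status. The population definitions (SAP 3.3) and the observed-case efficacy summaries (SAP 3.9.1) do not use medication dates, and no covariates (3.5) or subgroups (3.8) are planned.

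**The case against.** The strongest defence is that little in the planned output depends on these dates, and most of it stands.

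- **New starts.** A reader might infer that the tables will show antidepressants newly started with SPN-820. They will not: SAP 4.5 summarises by ATC class and preferred name, with no table of start dates or new starts. An ADT count by class and name is the same whatever start date is imputed.
- **All partial dates.** A reader might infer that any incomplete ADT date is moved to Day 1, or any incomplete stop date on study. Steps 2 to 4 show that the start must be year-only in the first-dose year, and the stop must be in the first-dose month.
- **Source data.** Table 3 sets an analysis date. Nothing says that it overwrites the eCRF entry, and the SAP does not say which date the listings show.
- **Deviations.** SAP 4.2 has potential important deviations reviewed before database lock and does not say that imputed dates generate them. No analysis population excludes subjects for them. False deviations could therefore be caught, but that review would not correct the concomitant table.
- **Rarity.** Washout is directed by the investigator after consent, eligibility is reviewed again on Day 1, and Protocol 9.3.3 provides for data queries. A missing stop day for such a drug should be uncommon, though not impossible.
- **Scope.** The title of Table 3 refers to concomitant medication, and SAP 4.5 names ADT separately, so applying the rule to ADT is an inference. The wording on non-study medication in Protocol 8.3 supports it.

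None of this makes the rule right where it does apply: it returns a date that the screening record already contradicts.

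**Conclusion.** The point holds as a minor one. As written, Table 3 misclassifies two kinds of medication record: a drug ongoing at first dose whose start is known only to the first-dose year, and a drug stopped before baseline in the first-dose month with the stop day missing. For an eligible ADT the first error is at least 43 days per affected record. For day-missing stops 1 to 28 days before Day 1, roughly half would be dated on or after Day 1 if gaps and calendar dates were evenly spread.

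The consequence is limited to prior/concomitant status in descriptive tables and listings, plus a possible query about prohibited medication. The number of records is unknown and probably small. The documents do not support reading this as a threat to the efficacy results or to the analysis populations.

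The conclusion rests on Table 3 covering ADT and on Day 12 as the last study date. The 43-day figure also rests on the 6-week requirement. Footnote m of the schedule in SAP 11.1 still states 4 weeks, which would give 28 + 1 = 29 days; the two passages need reconciling, but the point does not depend on which applies. One further ambiguity: Table 3 does not say whether the second start-date condition uses the raw or the imputed end date. If imputed, a stopped drug with both dates partial could be given a Day 1 start as well as an on-study end.

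**What to change.** Keep Table 3 for adverse events and add a medication rule:

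- **Start dates.** For medications recorded at screening as prior or ongoing, impute the earliest date consistent with the known parts, and no later than the screening date.
- **End dates.** For drugs documented as stopped before baseline, cap the imputed end date at the day before first dose.
- **No imputation from eligibility.** Do not derive the ADT start from the 6-week requirement. That would assume compliance with Inclusion 8 and could hide a violation.

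The cost is a few lines of SAP text and programming. The rule relies on the screening medication record and on documented stop status. The documents do not describe the eCRF field that would carry stop status, so its availability should be confirmed before the wording is fixed.

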3.10. Visit Windows

Unless otherwise specified, data will not be analyzed using visit windows; instead, nominal visits will be used. Deviations from protocol-specified visit windows will be recorded and displayed in data listings.

3.11. Interim Analyses

No interim analyses are planned.

4. STUDY SUBJECT AND EXPOSURE

4.1. Subjects Disposition

Subject disposition will be summarized descriptively using the number and percentage.

The disposition table will include the following categories:

- Number of subjects screened.
- Number of subjects in the specified population (i.e., Safety, FAS, PK and PD)
- Number (%) of subject who completed the study in the specified population
- Number (%) of subject who discontinued the study as well as the primary discontinuation reasons as recorded in the eCRF in the specified population

Inclusion and exclusion criteria met/not met and reasons for screen failures will be summarized in a separate table. A listing of subject disposition will be provided.

4.2. Protocol Deviations

A protocol deviation is defined as any change, divergence, or departure from the study design or procedures defined in the protocol. An important protocol deviation (IPD) is defined as a protocol deviation that might significantly affect the completeness, accuracy, and/or reliability of the study data or that might significantly affect a subject's rights, safety, or well-being.

Potential IPDs may include, but are not limited to:

- Subjects who received the study treatment but are later found not to have met all the inclusion criteria or met any of the exclusion criteria
- Subjects who received concomitant medications that were prohibited as described in Protocol Section 5.7

Occurrence of any of these and other events may be considered as potential IPDs. However, these events should be categorized as IPDs only if they could potentially affect interpretation of study results. Prior to the database lock, potential IPDs identified in the clinical database and/or recorded in the site deviation log will be reviewed for the determination of IPDs. All protocol deviations will be provided in subject data listings.

4.3. Demographic and Baseline Characteristics

Subject demographics and characteristics will be summarized descriptively using the Safety Population. Demographic includes age in years, age group (18-45, 46-65), sex, race, and ethnicity. Baseline characteristics includes height, weight, body mass index (BMI), and other pre-dosed baseline efficacy measurements (i.e. HAM-D₆, MADRS, and CGI-S total scores).

4.4. Medical History

Medical history will be coded using the Medical Dictionary for Regulatory Activities (MedDRA) version v26.1. The number and percent of subjects reporting various medical, family, and

psychiatric histories, grouped by system organ class (SOC) and preferred term (PT), will be summarized descriptively using the Safety Population. The table will be sorted by descending frequency of SOC and then PT within SOC. All medical and psychiatric history will be listed.

4.5. Prior and Concomitant Medications

Prior and concomitant medications and antidepressant therapy (ADT) will be coded using WHO DRUG Global version SEP2023 with anatomical therapeutic chemical (ATC) classification and Preferred Name (PN). ATC fourth (ATC4) level is for the chemical, pharmacological or therapeutic subgroup. If a ATC4 level classification is not available for a coded term, the lowest available ATC level code will be substituted.

If a medication starts prior to the first dose and continues after the first dose, it will be considered both prior and concomitant. Prior and concomitant medications as well as ATDs will be summarized by ATC and PN, and also listed by subject ID using the Safety Population.

4.6. Study Treatment Exposure

Duration of exposure for each subject is defined as:

- Duration of Treatment Exposure = date of last dose – date of first dose + 1.

The number (%) of subjects been dosed at each visit and the duration of exposure (days) will be summarized descriptively. A listing of treatment exposure will also be provided.

5. EFFICACY ANALYSES

All efficacy data will be summarized descriptively using the FAS and listed using the Safety Population.

5.1. Primary Efficacy Endpoint

The Hamilton depression rating scale is one of the most widely used clinician-administered depression scales. The original version contains 17 items related to symptoms of depression over the past week developed for hospital inpatients. The HAM-D₆, a subscale version with 6 items derived from the 17 items of the original scale, offers sensitivity for measuring severity of detecting improvement of depression comparable to other more complex versions. Five of the 6 items (Depressed Mood, Work and Activities, Feeling of Guilt, Anxiety Psychic, and Retardation) are scored on a scale of 0 to 4, and 1 item (Somatic Symptoms General) is scored on a scale of 0 to 2, for a possible total score of 0 to 22. If any item score is missing, the total score will not be calculated. A total score ranging 0-4 indicates that the subject is in the normal range (no depression), a score ranging 5-8 indicates “mild depression”, 9-12 indicates “moderate depression”, and 13-22 indicates “severe depression”.

CFB in the HAM-D₆ total score will be analyzed descriptively at each time point using the FAS.

5.2. Secondary Efficacy Endpoints

[figure not shown]
The MADRS is a 10-item investigator-rated diagnostic questionnaire used to measure the severity of depressive episodes in subjects with mood disorders and is designed to be sensitive to changes brought on by treatment. Each question is scored from 0 to 6, the sum of the 10 subtests score will yield a total score ranging from 0 to 60. If any item score is missing, the total score will not be calculated. A total score ranging from 0 to 6 indicates that the subject is in the normal range (no depression), a score ranging from 7 to 19 indicates “mild depression”, 20 to 34 indicates “moderate depression”, and 35 to 60 indicates “severe depression”.

[figure not shown]
The CGI-S is evaluated on a 7-point scale, where 1 = Normal, not at all ill, 2 = Borderline mentally ill, 3 = Mildly Ill, 4 = Moderately ill, 5 = Markedly ill, 6 = Severely ill, and 7 = Among the most extremely ill patients.

CFB to each time point in the MADRS total score and CGI-S score will be analyzed using descriptive statistics.

Percent reduction, defined as $100 \times (\text{postbaseline} - \text{baseline}) / \text{baseline}$, in MADRS total score will be derived for each subject.

The n (%) of responders (i.e., subjects with $\geq 50\%$ reduction in MADRS total score), the n (%) of subjects in remission (i.e., subjects with MADRS total score ≤ 10) and the n (%) of subjects with a CGI-S score of 1 or 2 will be summarized at each scheduled time point.

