3.2.2 Secondary Efficacy Endpoints

- Change from baseline to each time point in the MADRS total score.
- Change from baseline to each time point in the CGI-S total score.
- Proportion of subjects achieving a $\geq 50\%$ reduction from baseline in the MADRS total score.
- Proportion of subject in remission (MADRS total score ≤ 10) at each time point.
- Percentage of subjects with a CGI-S score of 1 or 2 at each time point.

■ [REDACTED]

■ [REDACTED].

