7.1.2 Montgomery-Åsberg Depression Rating Scale

The MADRS is a 10-item investigator-rated diagnostic questionnaire used to measure the severity of depressive episodes in patients with mood disorders and is designed to be sensitive to changes brought on by treatment ([Montgomery 1979](#)). Each question is scored from 0 to 6, the sum of the 10 subtests score will yield a total score ranging from 0 to 60. A higher MADRS score indicates more severe depression.

Successful therapy is indicated by a lower total score in subsequent testing (Montgomery-Åsberg Depression Rating Scale Past Week [Follow-Up Evaluation]).

There are 10 subtests based on each item:

1. Reported sadness
2. Apparent sadness
3. Inner tension
4. Reduced sleep
5. Reduced appetite
6. Concentration difficulties
7. Lassitude
8. Inability to feel
9. Pessimistic thoughts
10. Suicidal thoughts

The rater will use a structured interview that standardizes the administration of the 10 MADRS items known as structured interview guide for the MADRS, a structured interview was developed by [name] and [name] in order to increase inter-rater reliability, thus improving signal detection ([Williams 2008](#)).

The Standard (including comparison to euthymic baseline for 3 items) and Past Week versions will be administered, with the Standard Version administered at screening and the Past Week Version administered on days 1, 4, 7, and 10. Euthymic baseline is auto populated based on the information captured at the first administration.

The scale is a ClinRO administered by a qualified rater at all clinic visits.

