8.10.2 Secondary

The change from baseline at each time point in the MADRS and CGI-S total scores will be analyzed using descriptive statistics. Analyses for responders (proportion of subjects achieving a $\geq 50\%$ reduction from baseline in the MADRS total score), remission (proportion of subjects achieving MADRS ≤ 10 total score), and percentage of subjects with a CGI-S score of 1 or 2 will be summarized. The secondary efficacy analyses will be performed using the FAS population.

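### SAP 5.2 reverses the sign of percent reduction, so the MADRS responder rule, applied as written, counts no true responder and only subjects whose score rises by at least half

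*SAP*

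**What the plan says.** SAP 5.2 sets up the MADRS response analysis in two steps. It first specifies a variable to be calculated for every subject: "Percent reduction, defined as $100 \times (\text{postbaseline} - \text{baseline}) / \text{baseline}$, in MADRS total score". The following paragraph then counts as responders "subjects with $\geq 50\%$ reduction in MADRS total score", at each scheduled time point.

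The protocol states the endpoint in words only. Section 3.2.2 lists "Proportion of subjects achieving a $\geq 50\%$ reduction from baseline in the MADRS total score", and section 8.10.2 repeats the same rule. Neither section gives a formula, and protocol 8.1 leaves full analytical detail to the SAP.

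The direction of the scale is explicit in protocol 7.1.2: "A higher MADRS score indicates more severe depression", and "Successful therapy is indicated by a lower total score in subsequent testing". SAP Table 1 words the endpoint as the protocol does, and SAP section 9 declares no departure from the protocol's planned analyses.

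**The concern.** The label and the formula in SAP 5.2 point in opposite directions. A quantity called percent reduction should be positive when the score goes down. The one defined subtracts baseline from the post-baseline value, so it is positive only when the score goes up. Combined with a threshold of +50, it selects subjects who have deteriorated by half or more.

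MADRS response is one of five secondary efficacy endpoints. The trial is single-group and descriptive, with no hypotheses (SAP 3.6) and no power calculation (SAP 2.6), so the tabulated counts are themselves the results. If the variable is programmed as defined, the response table is meaningless. Even if the responder flag is coded by intent, a listed variable named percent reduction would show negative values for everyone who improved.

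**Working it through.** **Inputs**
- Formula, SAP 5.2: R = 100 × (P − B) / B, with B the baseline and P the post-baseline MADRS total.
- Responder rule, SAP 5.2: R ≥ 50.
- Scale range, SAP 5.2: "the sum of the 10 subtests score will yield a total score ranging from 0 to 60".
- Minimum baseline, protocol 4.2.2 inclusion criterion 6: 22.
- Remission rule, SAP 5.2: total score of 10 or less. It does not use the formula.

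The documents print no worked value or expected response rate, so there is no figure of the plan's own to reproduce.

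**Algebra**
- As written: 100 × (P − B) / B ≥ 50 is the same as P ≥ 1.5 × B.
- As intended: 100 × (B − P) / B ≥ 50 is the same as P ≤ 0.5 × B.

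For any B above zero these two sets cannot overlap. For a subject who does not worsen (P ≤ B), the largest value the written formula can take is 0.

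**Worked pairs**

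| Baseline → post | As written | Meets ≥ 50? | Sign corrected | Meets ≥ 50? |
|---|---|---|---|---|
| 22 → 11 | −50.0 | no | +50.0 | yes |
| 30 → 15 | −50.0 | no | +50.0 | yes |
| 30 → 12 | −60.0 | no | +60.0 | yes |
| 30 → 10 (remission) | −66.7 | no | +66.7 | yes |
| 30 → 30 | 0.0 | no | 0.0 | no |
| 24 → 36 | +50.0 | yes | −50.0 | no |
| 22 → 33 | +50.0 | yes | −50.0 | no |
| 30 → 45 | +50.0 | yes | −50.0 | no |
| 40 → 60 | +50.0 | yes | −50.0 | no |
| 41 → 60 | +46.3 | no | −46.3 | no |

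**Full grid.** Baselines 22 to 60 (39 values) and post-baseline scores 0 to 60 (61 values) give 39 × 61 = 2379 pairs.
- True responders (score at least halved): 829.
- Pairs meeting the rule as written: 271, all worsenings of at least 50%.
- Pairs in both groups: 0.
- Pairs in remission: 39 × 11 = 429, of which 0 meet the rule as written.
- With the sign corrected, all 829 halvings are classed as responders and no worsening is.

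Because the scale stops at 60, P ≥ 1.5 × B is possible only for B ≤ 60 / 1.5 = 40. A subject with a baseline above 40 could never be counted under the written rule.

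**Illustration.** Suppose 20 of the roughly 40 planned completers truly responded. The 20 is an assumption; the documents give no expected rate. The true rate is 20/40 = 50%. As written, none of those 20 is counted, and the table shows 0% plus any subject whose score rose by half.

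**The case against.** The strongest reply is that nobody would be misled. The responder rule is in words, and a subject whose score rises has no reduction in any ordinary sense. SAP Table 1, protocol 3.2.2 and protocol 8.10.2 all say reduction, protocol 7.1.2 fixes the direction of the scale, and SAP section 9 says nothing has changed from the protocol. A literal coding would also expose itself. With a baseline of at least 22, anyone at 10 or below has fallen by at least 100 × (22 − 10) / 22 = 54.5%, so every remitter must be a responder. A table with remitters and almost no responders would look impossible at once. The scope is narrow too: no test, decision rule or sample size depends on this variable.

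Much of this stands. The intended direction is clear, the error would probably be noticed, and nothing here shows that any output is wrong. But the wording elsewhere shows intent without repairing the formula. SAP Table 2, where derivations are collected, does not define the quantity, and no rule of −50 or lower appears anywhere. Nor is this just a loose label, since SAP section 7 uses the term percent change for BDNF. A programmer who follows the SAP gets the wrong answer, and one who follows the intent departs from the written specification. If two independent programmers differ, no other formula in the documents settles the matter.

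**Conclusion.** The point holds. SAP 5.2 defines percent change, calls it percent reduction and pairs it with a positive threshold. Applied as written, the rule excludes every subject whose MADRS score at least halves and admits only those whose score rises by at least half. The reported rate would not be the complement of the true rate. It would be close to zero regardless of the true rate.

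The consequence depends on the formula being programmed literally; the error in the specification does not. The separation of the two groups is algebraic and holds for any positive baseline, so it does not rest on the entry minimum of 22. The damage is confined to the derived percent-reduction variable, its listing and the MADRS responder proportion. The HAM-D6 primary endpoint, MADRS change from baseline, remission and the CGI-S endpoints do not use the formula. It should still be corrected, because it is the sole operational definition of a listed efficacy endpoint.

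**What to change.** In SAP 5.2, define percent reduction as 100 × (baseline − postbaseline) / baseline and keep the responder threshold at ≥ 50. Alternatively, leave the formula as it is, rename the quantity percent change, and define a responder as a value ≤ −50. Use one convention throughout the derivation, the listing and the table footnote.

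The cost is one line of SAP text and a version-history entry. The protocol wording is already right and needs no amendment, and no new data are needed. If programming has started, check the derived variable, its listing and the responder flag against the corrected line. A simple test is that every subject with a baseline of at least 22 who is in remission must also be flagged as a responder at that time point.
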